15.1.1 Response according to RECIST 1.1

[figure not shown]
Response in solid tumor cancers will be assessed in accordance with the RECIST criteria version 1.1^2 .

Table 4. Evaluation of Response

Target Lesions	Non-target Lesions	New Lesions	Response
CR	CR	No	CR
CR	Non-CR/Non-PD	No	PR
CR	Not evaluated	No	PR
PR	Non-PD or not all evaluated	No	PR
SD	Non-PD or not all evaluated	No	SD
Not all evaluated	Non-PD	No	NE
PD	Any	Yes or No	PD

TPL N°: eTPL SA-02-01 TPL Version: 02 Of SOP SA-02.08

TPL Effective Date: 31 Mar 2016 Approved in Vault: 6/30/2021

Any	PD	Yes or No	PD
Any	Any	Yes	PD

Confirmation:

PR and CR: changes in tumor measurements that are confirmed* by repeat assessments performed no less than four weeks after the criteria for response are first met are called confirmed responses. Onset of PR or CR without such confirmation is called unconfirmed.

SD: follow-up measurements must have met the SD criteria at least once and for a minimum time period of 6 weeks (\pm 7 days) after first treatment.

In the dose-escalation, response evaluation will be performed by the investigator. In the expansion, response evaluation will be performed by the investigator as well as a group of external medical experts, the independent review committee (IRC). Each subject will be assigned one of the following categories for each assessment:

- 1) CR,
- 2) PR,
- 3) SD,
- 4) PD, or
- 5) Not Evaluable (NE)

The best overall response is the best response recorded from the start of the treatment until disease progression/recurrence.

A subject is defined as an objective responder if he/she has a best overall response assessment of CR or PR.

Subjects in response categories 3, 4 and 5 (SD, PD or NE) are considered as non-responders.

Subjects with a best overall response assessment of CR, PR or SD are considered to be in disease control.

Confirmed* responses and all responses (including confirmed and unconfirmed responses) will be presented separately for the objective response (yes/no) and disease control (yes/no) parameters.

- [* The following sequences (assessments over time) will be counted as confirmed response:
 - CR-CR = CR confirmed
 - PR-PR = PR confirmed
 - PR-CR = PR confirmed

Note: the sequence CR-PR is not allowed and should be queried. The PR should be corrected to PD because of reappearance of disease. Imaging charter must make sure that prior scan is corrected to PR if believed when seeing the following scan to be only PR. This way CR-PR should not occur if the reader interprets this as a PR confirmed. Otherwise it would be CR-PD which would qualify as confirmed SD for the confirmed visit response if minimum duration criteria for SD is met.

TPL N°: eTPL SA-02-01 TPL Version: 02 Of SOP SA-02.08

TPL Effective Date: 31 Mar 2016 Approved in Vault: 6/30/2021

Intermediate missing (NE) scan evaluations between the response scan and the confirmation scan are allowed, e.g. the sequences PR-NE-PR and PR-NE-PR will be considered PR confirmed.

In all cases the scan that confirms the first scan with CR/PR must occur no sooner than 4 weeks after the first scan.

A subject with sequences that qualify both as PR confirmed and CR confirmed, e.g. PR-PR-CR-CR would be considered a CR confirmed. Note that the date of confirmed response will be the date of the first PR.

If PR or CR are not confirmed, the PR or CR response will be SD when the scan is on or after 35 days and NE when the scan is before 35 days. The 35 days takes into account the minimal 6-weeks duration +/-1 week window.]

A forest plot including the subgroups defined for cohorts 2 and 8 and for cohort 6 as mentioned in section 4.4 will be presented for investigator.

BOR and CBOR based on IRC data will be listed only. All other IRC results will not be included in the analysis. They will be kept in the derived datasets.

15.1.2 Response according to CA-125

Subjects with ovarian cancer will also be evaluated according to CA-125.

A CA-125 response (PR) is defined as at least a 50% reduction in CA-125 levels from a pretreatment sample. The response must be confirmed and maintained for at least 28 days. Subjects can be evaluated according to CA-125 only if they have a pretreatment sample that is at least twice the upper limit of the reference range and within 2 weeks before starting the treatment.

More information on the rules that apply to the CA-125 data is available in section 10.4 of the protocol final version 10.0, dd. 9 December 2019.

The date when the CA-125 level is first reduced by 50% is the date of the CA-125 response.

To calculate response, an analysis should be used that includes all subjects with an initial CA-125 level of at least twice the upper limit of the reference range as eligible and evaluable.

In addition, as a separate analysis, those subjects who have a CA-125 response and whose CA-125 level falls to within the reference range can be classified as CA-125 complete responders. Subjects who have a fall of CA-125 to within the reference range but whose initial CA-125 was less than twice the upper limit of the reference range have not had a CA-125 response and cannot therefore be classified as a CA-125 complete responder.

The best overall response for both parameters (CA-125 response and CA-125 complete response) will be presented.

15.1.3 Response according to RECIST 1.1 and CA-125 combined (Ovarian cancer only) – Expansion Part

For subjects with ovarian cancer in the expansion part, responses will also be evaluated and reported according to RECIST 1.1 in combination with CA-125 as defined by the Gynecological Cancer Intergroup³ (see table 5).

TPL N°: eTPL SA-02-01 TPL Version: 02 Of SOP SA-02.08

OF SOP SA-02.08

TPL Effective Date: 31 Mar 2016

Approved in Vault: 6/30/2021

Table 5. Best Overall Response in Subjects with Initial Measurable Disease and Evaluable by CA-125, combining both criteria

Non Target #	New Lesion	CA-125	Overall Best Response	Best
CR	No	Normal	CR	RECIST 1.1 response
Non-CR Non-PD	No	Not PD	PR	for CR and PR also requires
CR	No	PR but not normal	PR	it to be confirmed and
NE	No	PR	PR	maintained for
Non-PD or NAE	No	Not PD	PR	at least 28 days if response
Non-PD	No	PR	PR	is primary end point
PD or New >28 days from		PR	PR	
CA-125 PR *	:			
Non-PD	No	PR	PR	
Non-PD or NAE	No	Not PR and not PD	SD	
•	ys from	PR	PD	
CA-125 PR*	T			
Any	Yes or No	Any	PD	
PD	Yes or No	Any	PD	
Any	Yes	Any	PD	
Any	Yes or No	PD	PD	
	Target # CR Non-CR Non-PD CR NE Non-PD or NAE Non-PD lew > 28 day CA-125 PR * Non-PD Or NAE ew ≤ 28 day CA-125 PR* Any PD Any	Target # Lesion CR No Non-CR No Non-PD CR No NE No Non-PD No or NAE Non-PD No lew >28 days from CA-125 PR * Non-PD No or NAE ew ≤ 28 days from CA-125 PR* Any Yes or No Any Yes	Target # Lesion CR No Normal Non-CR No Not PD CR No PR but not normal NE No PR Non-PD No Not PD Iew > 28 days from PR CA-125 PR * Non-PD No Not PR Non-PD No PR Non-PD No PR CA-125 PR * Any Yes or No Any Any Yes or No Any Any Yes or No Any Any Yes or No Any	Target # Lesion Response CR No Normal CR Non-CR Non-PD No Not PD PR CR No PR but not normal PR NE No PR PR Non-PD No Not PD PR Non-PD No PR PR PR PR PR CA-125 PR * No Not PR and not PD Non-PD No Not PR and not PD SD ew ≤ 28 days from CA-125 PR* PR PD Any Yes or No Any PD Any Yes or No Any PD

 $[\]sim$ target lesions include up to 5 measurable lesions (2 per organ) as defined by RECIST 1.1.

Source: Definitions for Response and progression of ovarian cancer incorporating RECIST 1.1 and CA-125 agreed by the Gynaecological Cancer Intergroup (GCIG) – Rustin et All^3

TPL N°: eTPL SA-02-01 TPL Version: 02 Of SOP SA-02.08

TPL Effective Date: 31 Mar 2016

Approved in Vault: 6/30/2021

[#] non-target lesions include ascites and peritoneal thickening which are not measurable according to RECIST 1.1.

^{*} subjects who have a CA 125 response that occurs more than 28 days from PD according to RECIST 1.1 are considered a PR, according to best response, but PD if the RECIST 1.1 PD is within 28 days of CA 125 response. § the minimum time interval between 2 measurements for classification as stable disease is 6 weeks (± 7 days).

NE, Not evaluated; NAE, not all evaluated.

Best overall responses by investigator will be tabulated as in the example of the guideline³.

Progression or Recurrence based on serum CA 125 levels (PD in the table above) will be defined on the basis of a progressive serial elevation of serum CA 125, according to the following criteria:

A. Subjects with elevated CA-125 pretreatment and normalization of CA-125 must show evidence of CA-125 greater than, or equal to, two times the upper normal limit on two occasions at least one week apart or

Version: 4.0

- B. Subjects with elevated CA-125 pretreatment, which never normalizes must show evidence of CA-125 greater than, or equal to, two times the nadir value on two occasions at least one week apart or
- C. Subjects with CA-125 in the normal range pretreatment must show evidence of CA-125 greater than, or equal to, two times the upper normal limit on two occasions at least one week apart.

In the listing of CA-125 a flag to indicate if the CA-125 fulfills the response ("PR"), "PD" or "Not PR or PD" -criteria will be added.

15.1.4 Progression-Free Survival according to RECIST 1.1

PFS is defined as the number of days from the date of first IMP administration to first PD or death whichever occurs first.

PFS will be derived for all subjects and presented graphically as well as summarized using survival analysis methods:

- Kaplan-Meier curves
- Kaplan-Meier curves by subgroups defined for cohorts 2 and 8 and for cohort 6 as mentioned in section 4.4
- Kaplan-Meier estimates.
- Kaplan-Meier estimates by subgroups defined for cohorts 2 and 8 and for cohort 6 as mentioned in section 4.4.

PFS will be censored in accordance with Table A in Appendix 3 in the FDA Guidance for Industry "Clinical Trial Endpoints for the Approval of Cancer Drugs and Biologics (2007)".In summary, PFS will be censored if no event (progression or death) is observed before the first of (i) the analysis cut-off date, and (ii) the date when a new anti-cancer therapy is started. The censoring date will be the date of the last adequate tumor assessment prior to cut-off/start of new anti-cancer therapy. In case of an event after 2 or more missed scans, censoring will be done at last adequate tumor assessment date before the missed scans (Censoring rule based on FDA guideline). Two scans are considered missing if no evaluable response result (CR, PR, SD or PD) is available within a period of 98 days (6+1 weeks times 2) for 1Q3W dose schedule and a period of 126 days (8+1 weeks times 2) for 3Q4W dose schedule.

[figure not shown]

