In order to obtain sufficient evaluable fresh tumor biopsies, up to 15 additional patients may be recruited in Cohort 6 to ensure that 25 fresh biopsies are acquired. A maximum of 45 patients may therefore be enrolled in Cohort 6. A higher number of biopsies are required in this cohort due to the mixture of tumor types being enrolled.

Cohort 8 will further explore the safety and efficacy of the 1.0 mg/kg 3Q4W schedule in NSCLC patients without EGFR/ALK mutations. This is the same patient population as Cohort 2 where a preliminary efficacy signal was observed for the 1Q3W schedule. Cohort 8 will include up to 37 patients with the aim to collect evaluable fresh tumor biopsies from 15 patients. Recruitment is not linked to the number of biopsies collected and may continue up to a maximum of 37 patients even if 15 fresh tumor biopsies have already been obtained. The benefit/risk balance will be evaluated on an ongoing basis in this cohort.

An interim analysis for futility will be performed after 22 patients per cohort (minus Cohorts 6 and 8) if there are < 15 patients with evaluable fresh biopsies in the corresponding cohort. Based on the results, further recruitment to the corresponding cohort may be stopped.

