Pregnancy Test	X	X						X				X			X	X			X 
ADA (Immunogenicity)		X 						X 							X	X			X 
Hepatitis B, C, CMV 	X														X				X 
PK Sampling	Please refer to Section 8.2 for details of PK samplings																		
Tumor biopsy	X 																		X 
Biomarkers	X		X 								X 				X				
Patient diary handout		X						X											
Patient diary collection		X 						X				X 			X				
Review of patient diary data		X 	X	X	X	X	X	X	X	X	X	X 			X				

Footnotes to Trial Flowchart – Dose Escalation 3Q4W
1 If the patient shows PD, is to start new anti-cancer treatment or withdraws from treatment due to another reason the End of treatment visit should be performed as soon as possible after decision of withdrawal.
2 The visit windows relate to the day of the previous visit. Visit 1 of Cycle 3 and onwards should be performed 7 days ±3 days after Day 22 of the previous cycle.
3 Visit window not applicable for C1V1 and C2V1.
4 Signs, symptoms and diagnosis occurring between Visit 0 and first infusion should be recorded as medical history (see Section 8.4 for details). SAEs should be reported as of the signing of the informed consent.
5 Body weight will be measured on the first dosing day in a cycle, as part of the dose calculation. If body weight is assessed ≤ 7 days before the first day of the planned dosing in a cycle, this weight can be used to calculate dose and is the weight recorded in the eCRF.
6 Temperature, blood pressure and heart rate as according to Section 8.4.8.

Document Name: GCT1021-01 Protocol

Document Number: TMF-03326

Version: 11.0

Footnotes to Trial Flowchart – Dose Escalation 3Q4W
7 All patients will have a CT-scan with contrast of thorax, abdomen, and pelvis performed as part of the screening procedure. If a CT-scan has been performed within 28 days prior to visit CIV1 as part of standard procedure, it is acceptable as screening CT-scan for the trial. If there is suggestion of brain metastases/tumors, a CT-scan of the head will be performed before inclusion.
8 Radiological assessments are to be performed every 8 weeks from CID1. See Section 8.4.7.
9 To be completed as indicated to confirm response, new symptoms, end of treatment visit or at the physician discretion see Section 8.4.7.

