**Footnotes to Trial Flowchart – Expansion**

- 1 If the patient shows PD, is to start new anti-cancer treatment or withdraws from treatment due to another reason the End of treatment visit should be performed as soon as possible after decision of withdrawal.
- 2 The visit windows relate to the day of the previous visit. Visit 1 of Cycle 2 and onwards should be performed 7 days ±3 days after Day 15/22 of the previous cycle.
- 3 Signs, symptoms and diagnosis occurring between Visit 0 and first infusion should be recorded as medical history (see Section 8.4 for details). SAEs should be reported as of the signing of the informed consent.
- 4 Body weight will be measured on the first dosing day in a cycle, as part of the dose calculation. If body weight is assessed ≤ 7 days before the first day of the planned dosing in a cycle, this weight can be used to calculate dose and is the weight recorded in the eCRF.
- 5 Temperature, blood pressure and heart rate as according to Section 8.4.8.
- 6 All patients will have a CT-scan with contrast of thorax, abdomen, and pelvis performed as part of the screening procedure. If a CT-scan has been performed within 28 days prior to visit CIV1 as part of standard procedure, it is acceptable as screening CT-scan for the trial. If there is suggestion of brain metastases/tumors, a CT-scan of the head will be performed before inclusion. Clinical measurement in case of superficial cutaneous lesions should be performed within 28 days prior to visit CIV1 as part of standard procedure. For further details on imaging please refer to Section 8.4.7.
- 7 Radiological assessments and clinical measurements of superficial cutaneous lesions are to be performed every 6 (1Q3W and Cohort 8 3Q4W) or 8 (Cohort 6 3Q4W) weeks (±7days) from C1D1 until disease progression. If treatment is discontinued prematurely, prior to detection of disease progression (e.g., due to an adverse event), every effort should be made that scans continue according to the protocol until disease progression, start of a new anti-cancer treatment, withdrawal of consent or death (see Section 8.4.7 for details).
- 8 To be completed as indicated to confirm response or new symptoms at the end of treatment visit or at the physician discretion.
- 9 TSH, T3 and T4 will only be measured at screening and on Visit 1 of every even cycle.

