#### 8.4.7 Imaging/Computed Tomography

All patients will have a CT-scan with contrast of thorax, abdomen and pelvis performed during screening. If there is suspicion of brain metastases/tumors, a CT-scan of the head will be performed before inclusion. For patients with stable brain metastases enrolled in the expansion part, the CT-scan must include the head and neck.

For patients with superficial cutaneous lesions that are not measurable by a CT-scan, measurement using calipers can be performed, using photographs as documentation.

All sites of metastatic disease should be reported at baseline and followed throughout the trial. Up to 5 target lesions (maximum two per organ) will be defined at screening. A lesion from which a fresh biopsy has been taken during the trial cannot be a target lesion.

Baseline imaging assessments will be performed during the screening period. Any imaging assessments already completed for regular radiographic evaluation of the patient's cancer can be considered as the baseline images for this trial, as long as they are of sufficient diagnostic quality and have been obtained ≤ 28 days prior to C1D1.

Post-baseline scans will be performed every 6 weeks (1Q3W and Cohort 8 3Q4W) or 8 weeks (Cohort 6 3Q4W) (±7 days) from C1D1 until investigator assessed disease progression according to RECIST v1.1. Time points for radiographic evaluation should be calendar based and do not depend on cycle visits i.e. radiological evaluation should be performed regardless of IMP administration delays. For patients who permanently discontinue IMP for other reasons than disease progression (e.g., adverse events), every effort should be made to continue on-trial radiological evaluation according to protocol until disease progression, start of a new anti-cancer treatment, withdrawal of consent or death (see [Table 11](#)).

Document Name: GCT1021-01 Protocol

Document Number: TMF-03326

Version: 11.0

---

If reduction of target lesions  $\geq 30\%$  in size is observed a repeat CT-scan will be performed after 4 (in particular for the 3Q4W-arm) to 6 weeks (in particular for the 1Q3W-arm) to confirm the response.

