For the dose-escalation part, all seven dose levels from the 1Q3W regimen together with a 'total' will be presented on one page. And similar for the 3Q4W regimen in the dose-escalation part, all four dose levels will be presented together on one page including a 'total'.

For the expansion part the following grouping should be done: Cohorts 1, 3, 4, 5, 6 and 7 on one page and cohort 2 with 2.2 mg/kg, cohort 2 with 1.8 mg/kg, cohort 2 total, cohort 8, total across 1Q3W and total across 3Q4W on one page.

All data will be listed by trial part, cohort for expansion part, dose schedule, dose level, subject number and visit (if applicable).

In general, in plots where subject data are grouped together (e.g. plots of means), the ticks on the time-axis will denote the nominal visit numbers (e.g. Scr, C1D1, C1D2, C1D4 etc.) separated with distances proportionate to the difference between the time-points of the corresponding visits in the relevant dose schedule (cf. the Visit Number and Day/Week rows of table of assessments in section 8 of the protocol final version 10.0, dd. 9 December 2019). Unscheduled visit data will not be included. In plots where individual subject data are plotted vs. time, the time on the horizontal axis will denote the actual time since C1D1. Unscheduled visit data will be included in these plots.

In tables and listings presenting data by visit, the visit names (Screening, Cycle 1 Day 1, Cycle 1 Day 2, ..., End of Treatment, Safety Follow-up, Subject Follow-up and End of Trial) will be used or their abbreviated term (Scr, C1D1, C1D2, ..., EOTrt, Saf FU, Pat FU, EOTrial).

In tables and listings presenting coded data (medical history, prior and concomitant medications, adverse events, prior and subsequent cancer therapies), the dictionary and the version used will be mentioned in the footnote.

When data until a certain date needs to be included in the analysis, the cut-off date will be defined as this date. If no cut-off needs to be applied, the cut-off date will be defined as the date of data extraction.

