5.2 Protocol Deviations

The important major protocol deviations will be summarized. The details will be listed.

In addition, Covid-19 related PDs will be listed separately:

All important PDs related to Covid-19;

TPL N°: eTPL SA-02-01 TPL Version: 02

Of SOP SA-02.08
TPL Effective Date: 31 Mar 2016
Approved in Vault: 6/30/2021

- All non-important PDs related to Covid-19 (this will be major, non-important as well as minor, non-important);
- Subject listing of missed/changed visits;
- Subject listing of assessments missed due to visits impacted by Covid-19.

A summary table of the above might be added to evaluate the impact of Covid-19.

Protocol deviations will be defined in the protocol deviations plan.

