15.1.6 Duration of Confirmed Response (RECIST 1.1) - Expansion Part

Duration of confirmed response (DoR) is defined as the number of weeks from the first documentation of confirmed objective tumor response (CR or PR) to the date of first PD or death. DoR will be analyzed using the same statistical methodology as PFS and the same censoring rules based on the FDA guideline, see section 15.1.4. DoR will be presented using confirmed responses only. Both the response assessments from the investigator will be presented.

15.1.7 Time to RECIST 1.1 and CA-125 combined response (Ovarian cancer only) – Expansion Part

Time to first RECIST 1.1 and CA-125 combined response (see Table 5 above) will be presented using the same statistical methodology as for ToR. CA-125 evaluation criteria (see section 15.1.2) should be fulfilled for CA-125 response evaluation, but not for RECIST 1.1 response evaluation (hence if they are NE based on CA-125, ovarian subjects are considered non-responder for CA-125 before defining the combined output). Both the response assessments from the investigator will be presented. The analysis will be performed for confirmed responses based on RECIST 1.1 only.

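### The two-missed-scans window for PFS and DoR follows the dosing schedule, so Cohort 8, scanned every 6 weeks, gets 126 days where the SAP's own formula gives 98

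*SAP*

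**What the plan says.** SAP 15.1.4 censors PFS at the last adequate assessment when an event comes after two or more missed scans. Two scans count as missed when no evaluable response result is available within "98 days (6+1 weeks times 2) for 1Q3W dose schedule and a period of 126 days (8+1 weeks times 2) for 3Q4W dose schedule". SAP 15.1.6 carries this over: "DoR will be analyzed using the same statistical methodology as PFS and the same censoring rules based on the FDA guideline".

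The protocol sets scan intervals separately from dosing. For the expansion part, Table 11 footnote 7 has scans "every 6 (1Q3W and Cohort 8 3Q4W) or 8 (Cohort 6 3Q4W) weeks", and section 8.4.7 agrees. For the 3Q4W escalation arm, Table 10 footnote 8 says "Radiological assessments are to be performed every 8 weeks from CID1". The 1Q3W escalation arm is scanned every 6 weeks (Table 9 footnote 8). SAP 4.5.2 places Cohort 8 on 3Q4W at 1.0 mg/kg.

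On the relation of Cohort 8 to Cohort 2, the protocol synopsis states: "This is the same patient population as Cohort 2 where a preliminary efficacy signal was observed for the 1Q3W schedule". SAP Section 4 puts them on one output page: "cohort 2 with 2.2 mg/kg, cohort 2 with 1.8 mg/kg, cohort 2 total, cohort 8, total across 1Q3W".

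As of Amendment 10, Protocol 16.2.7 and Table 31 footnote 7 move 1Q3W and Cohort 8 to 12-week scans and leave Cohort 6 at 8 weeks. SAP addendum sections 2.1 and 3.2 repeat PFS with the rules of SAP version 4.

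**The concern.** The terms 6+1 and 8+1 in the SAP show that the window is meant to be twice the scan interval plus its one-week tolerance. Dosing schedule stands in for scan interval, and that substitution fails for one group: Cohort 8 is 3Q4W but shares the 6-week scans of the 1Q3W cohorts. SAP 15.1.4 makes no exception for it, and SAP 4.9 (changes to protocol) does not mention the point.

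The result is that two cohorts with the same population and the same scan calendar, shown side by side, are described under different censoring rules. An event 99 to 126 days after the last evaluable scan is censored in Cohort 2 and counted in Cohort 8. This reaches the main CSR. It needs missed scans to have any effect, and the SAP foresees some, since it plans a "Subject listing of assessments missed due to visits impacted by Covid-19".

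**Working it through.** **Inputs.** Windows and their construction: SAP 15.1.4. Scan intervals and the ±7-day tolerance: Protocol 8.4.7, Tables 9-11, 16.2.7 and Table 31. Maximum size of Cohort 8, 37: Protocol 3.4. Trial end, 12 November 2021: SAP addendum 2.1. Amendment 10 issued 30 June 2021.

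**Step 1: reproduce the SAP's figures.** Window = 2 × (interval in weeks + 1) × 7 days.
- 6 weeks: 2 × 7 × 7 = 98
- 8 weeks: 2 × 9 × 7 = 126
- 12 weeks: 2 × 13 × 7 = 182

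Both printed figures are reproduced. Cohort 8 on 6-week scans should have 98.

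**Step 2: gap from the last evaluable scan to progression found at a scheduled scan.** With *m* scans missed and interval *k* weeks, the gap is 7*k*(*m*+1) days, ±14 because each of the two scans may shift by 7 days.

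| Interval | 1 missed | 2 missed | 3 missed |
|---|---|---|---|
| 6 weeks | 84 (70-98) | 126 (112-140) | 168 (154-182) |
| 8 weeks | 112 (98-126) | 168 (154-182) | 224 (210-238) |
| 12 weeks | 168 (154-182) | 252 (238-266) | 336 (322-350) |

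Reading the rule as a gap longer than the window:
- 6-week scans with 98 days: one missed scan is never flagged, two always are. This is right for the 1Q3W cohorts.
- 8-week scans with 126 days: the same. This is right for Cohort 6 and the 3Q4W escalation arm.
- 6-week scans with 126 days (Cohort 8): two missed scans straddle the limit, and only three are certain to be flagged.

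**Step 3: how often Cohort 8 escapes.** Assume each scan day is uniform on the integers -7 to +7. The two shifts are equal in 15 of 225 combinations, so P(gap > 126) = (1 - 15/225)/2 = 46.7%, and 53.3% escape. If a gap of exactly 126 days is also flagged, 46.7% + 15/225 = 53.3% are caught and 46.7% escape.

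**Step 4: expected size.** The documents give no missed-scan rate, so all inputs here are assumed: 37 patients, 6-week scans ±7 days, exponential time to progression with median 3 or 6 months, either no deaths or independent deaths with median 12 months, scans missed independently, 1500 simulated trials per setting.

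| Scans missed | Mean number whose status differs, 98 v 126 days | With new-therapy censoring (assumed median 6 months) |
|---|---|---|
| 5% | 0.08-0.10 | 0.04-0.05 |
| 10% | 0.26-0.39 | 0.12-0.19 |
| 20% | 0.91-1.29 | 0.40-0.58 |

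Without new-therapy censoring, the 6-month PFS rate moves by at most 0.4 percentage points on average. Missed scans that cluster within patients would raise the counts. DoR was not simulated; it concerns confirmed responders only.

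**Step 5: the addendum.** On 12-week scans one missed scan leaves 154-182 days, above both 98 and 126, so a single missed scan would be treated as two. With 182 days, one missed scan is never flagged and two always are. From 30 June to 12 November 2021 is 135 days, shorter than 154, so a full gap of this kind cannot fall wholly after the amendment was issued. What remains is a death, an unscheduled progression, or a gap that spans implementation. For example, week 42 scanned, week 48 missed and week 60 scanned gives 18 × 7 = 126 days nominally (112-140) after one missed scan.

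**The case against.** The strongest reply is that little follows. PFS and DoR are secondary endpoints, summarised by Kaplan-Meier estimates. No test of PFS and no formal comparison of Cohort 8 with Cohort 2 is planned; the formal tests in Protocol 10.2.3 are on response. Development had already been stopped. By the figures above, fewer than half a patient changes status at 5-10% missed scans. All of this stands and limits the point to a minor one. It does not make the window right.

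A second reply concerns the remedy. The CSR has been reported under SAP version 4, and Protocol 10.2.3 treats the CSR cut-off as the full efficacy result. Replacing a pre-specified censoring rule inside the addendum PFS would change it after results are known, and addendum and CSR would then differ for a reason other than new data. This also stands, and the fix respects it.

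Three stronger readings are tempting, and the documents do not support them:
- That the windows are wrong throughout. Before Amendment 10 they match the scan interval in Cohorts 1-7 and both escalation arms.
- That 98 days would catch every event after two missed scans. PFS events include deaths, and Protocol 8.4.7 allows unscheduled imaging. A patient who misses scans on days 42 and 84 after the last evaluable one and dies on day 93 is flagged under neither window.
- That the addendum PFS is invalid after the move to 12-week scans. At most 3 patients were still on treatment, their cohorts are not stated, on-time 12-week scans (70-98 days apart) do not exceed 98 days, and possibly no event is affected. DoR there appears only in a listing.

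**Conclusion.** The point holds for Cohort 8. SAP 15.1.4, and 15.1.6 by reference, give it 126 days where the SAP's own construction gives 98, and nothing elsewhere in the documents corrects this. For progression found at the scheduled scan after two missed ones, 47-53% of events escape the stated rule in Cohort 8, against none in Cohort 2. That range assumes uniform scan days and depends only on whether a gap of exactly 126 days is flagged.

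The likely effect on results is small: about 1 of at most 37 patients at 20% independently missed scans, well under 1 at 10% or less, and lower again with new-therapy censoring. The true missed-scan rate and the actual size of Cohort 8 are not in the documents. The side-by-side display should therefore not be read as materially distorted. It should be read as using two rules where one was intended.

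The carry-over of 98/126 days into the addendum is a minor note.

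**What to change.** 1. State the window by scan interval: 98 days for 6-week scanning (all 1Q3W groups, and Cohort 8 before Amendment 10) and 126 days for 8-week scanning (Cohort 6 and the 3Q4W escalation arm).
2. Report Cohort 8 PFS and DoR at the CSR cut-off under 98 days, as a labelled correction or sensitivity run beside the original result. If no patient changes status, one sentence saying so is enough.
3. In the addendum, keep the pre-specified PFS. For the at most 3 patients on reduced scanning, check whether any event was censored after only one missed scan, counting the scheduled scans where a gap spans the site's implementation of Amendment 10. If there is one, give the result under 182 days as a sensitivity analysis.

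The cost is a short paragraph, one rerun for Cohort 8, and the implementation dates for at most 3 patients. The addendum already reruns all derived datasets on the whole database, and no new patient data are needed.
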